#### Response:

We are using a crossover pre/post study design where seven after-school programs would receive the intervention in years 1 and 2 and seven schools would serve as matched comparison sites. During year two, the next seven schools would receive the intervention. This tiered approach begins with an initial assessment of the playgrounds to ensure that designs include the research-based elements of balancing, brachiating, climbing, spinning, sliding, and swinging. During years 1 & 2, Healthy School Staff will be trained with the xxx curriculum and the children will be trained as Peer Leaders (Fall Semesters 2022 and 2023) who are enrolled in the after-school program who then become peer leaders for all children during recess at their school.

Assessments include Physical, Social and Emotional Health Assessments administered fall and spring semesters of both years to track student behaviors. Assessments of the after-school setting will be conducted by Xplore program leaders on paper and include observations of all students attending Xplore programs. Assessments during recess would be conducted by recess aides/healthy school staff and would include a random sample of 25 students at recess. No identifying information will be recorded. Assessments will take approximately 5-10 minutes to complete. A copy of the assessment is included (K-6 Assessment).

We will ask the Healthy School Staff to complete a survey each fall and spring semester to learn about their perceptions of the training and playground activities. The survey will take approximately 5-10 minutes to complete. A copy of the staff assessment is included (Healthy School Staff Survey). Healthy School Staff may also be asked to participate in a 30-minute interview each spring semester.

We will ask students to complete a short survey about their physical, social, and emotional health and perceptions of the play activities in the program twice a year. The survey will take approximately 5-10 minutes to complete. A copy of the student assessment is included (Student Survey).

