We will also track student participants' physical activity patterns each semester via accelerometry (total of 4 times) for the 7 intervention schools student participants (n=147), and at the other 7 program schools during their control condition year (n=147). Students will wear ActiGraph GT3X+ accelerometer devices for 24 hours over a period of seven days twice a year. Three members of our research team will visit the after school program to set up the students with devices, and on the following week to collect the devices. Students will initially be shown how to secure the devices using the easy velcro wristband upon arrival at the program in the afternoon by the research team. Participants will wear accelerometers on their wrist to promote greater wear compliance compared to the hip among children. The match-box sized accelerometers are the most commonly used accelerometers in PA research and have been utilized by our research team in studies involving elementary schoolchildren. If a participant loses the accelerometer, they will be asked to immediately inform the front office staff who will inform our research team via email. Each child participant will be assigned a unique unidentifiable number (study ID) which will be linked to a person and used throughout the study.

Students may also be asked to participate in a small group interview for 15 minutes about the changes in their afterschool program at the end of each semester.

The research team will collect attendance, behavioral referral information at the school level without names. As well as demographic information for student participants only (gender, age, race/ethnicity) at all schools from the front office staff at the end of each semester to look for significant relationships between participation in the project and reduced behavior referrals as well as increase attendance. The school district personnel have agreed to the study design and measures. This data will only be collected for participants in this project.

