- 11.4 No identifying information will be stored, so extra protection for highly sensitive material is not warranted.
- 11.5 We will not obtain any audio or video recordings.
- 11.6 Consent and assent forms will be secured in a manilla envelope in a locked file cabinet in a locked room. They will be kept for 5 years. These forms will be kept separate from the rest of the data from the study.

11.7 We will use a master list of student IDs that will not be tied to any identifiable information. Any identifiable information included in this master list will be destroyed (deleted or shredded) as soon as the data are linked. These IDs will be used to link accelerometer devices to individual demographics such as sex and school.

11.8 No identifying information will be included in the research.

11.9 No secondary data will be utilized in this research.

11.10 We will not include any data covered under FERPA.

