A cluster randomized controlled trial of an after-school playground curriculum intervention to improve children's physical, social, and emotional health: Study protocol for the PLAYground project

NCT ID not yet assigned

Date: June 20, 2022

Statistical Analysis Plan

Data analysis

Intervention effects on the primary trial outcomes (at each follow-up time point) will be assessed using general linear mixed effects models to account for the clustering of individual measurements within schools. These will include fixed effects for treatment group (intervention vs control), time (baseline and follow-up), and interaction term (intervention x time); include school as a random effect; and be adjusted for covariates related to the outcome (eg, student sex, age). Analyses related to physical, social, and emotional health will be performed with the child (nested within a school) as the unit of analysis. Analysis related to attendance and behavioral change will be performed with the school as the level of analysis. Separate analyses will be performed at each follow-up time point. Schools will be included in analyses if they meet at least 80% adherence to the protocol.

Secondary implementation outcomes will be assessed using descriptive statistics for Healthy Staff and Student survey data (appropriateness and feasibility) and data from monthly observations (fidelity and sustainability). Frequencies, means, and standard deviations will be calculated to describe the distributions, measures of central tendency, and dispersion of item responses. Data from Healthy Staff and Student interviews will be analyzed using a matrix analysis to summarize and organize data in alignment with Proctor's dimensions (adherence, exposure/dose, quality of delivery, component differentiation, and participant involvement), and content analysis to identify salient themes for each school, by school-level income, and collectively among intervention school groups. We will utilize a deductive approach, but allow for additional themes to emerge.

Sample size calculation

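### For outcomes linked to the same child, the primary model names school as its only random effect, so the intervention x time standard error is generally wrong, in a direction the documents do not settle

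*SAP*

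**What the plan says.** The Data analysis section of the SAP holds the only model specification. It is a general linear mixed model with fixed effects for group, time (two levels) and their interaction, and covariates such as sex and age. The random part is given in the words "interaction term (intervention x time); include school as a random effect". Analyses of physical, social and emotional health "will be performed with the child (nested within a school) as the unit of analysis"; the next sentence puts attendance and behaviour at school level. "Separate analyses will be performed at each follow-up time point", so each model holds baseline plus one follow-up, and a linked child supplies up to two rows. "Schools will be included in analyses if they meet at least 80% adherence to the protocol", so 14 schools is a maximum. The SAP names no child effect, residual covariance, school-by-time effect, robust variance or degrees-of-freedom method.

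The protocol shows that at least one outcome is repeated on identifiable children. Under IRB 7 (Study Procedures): "Students will wear ActiGraph GT3X+ accelerometer devices for 24 hours over a period of seven days twice a year", and "Each child participant will be assigned a unique unidentifiable number (study ID) which will be linked to a person and used throughout the study". Under IRB 11, item 11.7: "These IDs will be used to link accelerometer devices to individual demographics such as sex and school". IRB 7 also describes recess observations on 25 randomly chosen pupils, recorded anonymously. Those are not linked by child and lie outside the main claim.

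**The concern.** The treatment effect is a difference between arms in change over time. Two sources of variation govern its standard error, and the stated model represents neither.

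- **Pairing within child.** A child's baseline and follow-up are correlated. With school as the only random effect they are treated as independent once the school is known. The gain from pairing is lost and the standard error is too large.
- **Variation between schools in change.** A school effect that is constant over time cancels from a change. If schools drift differently for reasons unrelated to treatment, that drift does not enter the standard error, although schools are the units allocated. The standard error is then too small.

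The errors pull in opposite directions, so the plan could lose real power or produce too many false positives. Which one occurs depends on quantities the team has not stated.

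**Working it through.** **The plan's own figure.** The SAP states a detectable effect of 0.370 with 147 children per arm, ICC 0.05, 80% power and alpha 0.05. With 21 children per school the design effect is 1 + 20 × 0.05 = 2.0, and (1.960 + 0.842) × sqrt(2 × 2.0 / 147) = 0.462. So 0.370 does not follow from the stated inputs. That is a separate matter; below, 0.370 serves only as the effect the SAP wants to detect.

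**Inputs from the SAP (Sample size calculation).** 7+7 schools; ICC 0.05; 294 children; 20% loss. 294 × 0.8 = 235, and 235 / 14 is about 17 children per school (m).

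**Assumed, because the documents are silent.** Total variance 1; within-child correlation r (defined within school) = 0.6; time-specific share s of the school variance = 0, 20, 50 or 100%; complete pairs; two-sided 5% test.

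**True standard error** of the difference in change:

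sqrt{ (2/7) × [2 × 0.05 × s + 2 × 0.95 × (1 − r)/m] }

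- s = 0: sqrt{0.2857 × 0.0447} = 0.113
- s = 100%: sqrt{0.2857 × (0.1 + 0.0447)} = 0.203

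**Standard error reported by the stated model.** About sqrt(4 × pooled within-school variance / children per arm) = sqrt(4 × 0.95 / 119) = 0.179. Simulation gives 0.177 to 0.179. It hardly moves with s.

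**Type I error** is 2 × [1 − Φ(c × model SE / true SE)], with c = 1.96 for z or 2.179 for 12 df. At s = 100% against z: 1.96 × 0.179 / 0.203 = 1.73, giving 8.4%.

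**Power of the stated model** is about Φ[(0.370 − 1.96 × model SE) / true SE]. At s = 0: (0.370 − 0.347) / 0.113 = 0.20, giving 58%.

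**Power of a school-level t test on mean change** comes from the noncentral t on 12 df with noncentrality 0.370 / true SE = 3.27 / 2.72 / 2.25 / 1.82.

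| Time-specific share | 0 | 20% | 50% | 100% |
|---|---|---|---|---|
| Model SE | 0.177 | 0.178 | 0.178 | 0.179 |
| True SE | 0.113 | 0.136 | 0.164 | 0.203 |
| Type I error, z | 0.2% | 1.1% | 3.4% | 8.4% |
| Type I error, 12 df | 0.1% | 0.5% | 1.9% | 5.5% |
| Power, stated model (z) | 58% | 56% | 55% | 54% |
| Power, school-level change test | 85% | 70% | 54% | 39% |

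Simulation agrees with these formulas within its error.

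**Sensitivity.**

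- *Lower r.* At r = 0.3, against z, type I error is 6.7% at a share of 50% and 11.8% at 100%.
- *Range of r.* Over r = 0.3 to 0.8, model SE divided by true SE runs about 1.2–2.2, 1.1–1.6, 0.94–1.24 and 0.80–0.95 at the four shares. The errors cancel at a share of about 0.34 (r = 0.3), 0.67 (r = 0.6) or 0.89 (r = 0.8).
- *21 per school.* If 294 is the number at follow-up, as the SAP says, type I error at r = 0.6 against z is about 0.2 / 1.3 / 4.5 / 11%.
- *Child intercept only.* Adding a child intercept and nothing else removes the first error and exposes the second: type I error is 10 / 17 / 25% at shares of 20 / 50 / 100% (r = 0.6).

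**The case against.** **The SAP is silent rather than wrong.** It never says intercept only, and calling the child nested within school is compatible with a child term. This stands in part: the team may intend more than it wrote. But the sentence about the child sets the level of the data, in contrast to the school-level outcomes that follow, and adds no correlation term. If it is read as a child intercept, between-school variation in change is still missing and the test is more liberal. Both readings need correction.

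**The false-positive figures assume a z test.** This stands as a limit. The SAP names no reference distribution; on 12 df the 8.4% becomes 5.5%.

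**The power gap is the extreme case.** This also stands. A reader might take 58% against 85% as the expected loss. It requires schools to change exactly alike, plus an assumed r of 0.6. At a share of 50% the two powers are level. At 100% the stated model's 54% is higher only because its test is too liberal.

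**Linkage is not fully secured.** Item 11.7 of IRB 11 has identifiers in the master list destroyed once data are linked, which leaves matching of fall to spring records less certain than IRB 7 suggests. The SAP also does not name accelerometry as primary. The claim is therefore limited to outcomes that are linked.

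**Complete pairs only.** The SAP expects 20% loss, and a mixed model would keep the baseline rows of children lost later. By formula, with 21 children at baseline and 17 at follow-up (r = 0.6), the stated model's power at share 0 is about 62% rather than 58%, and its type I error at share 100% is about 10%. The pattern is unchanged, but the exact figures do not carry over.

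**Conclusion.** The concern holds for outcomes measured at baseline and follow-up on the same ID-linked children. Fitted as written, the model gives an interaction standard error that is generally wrong. Under the assumptions above (ICC 0.05, r = 0.6, 17 per school, complete pairs) it runs from 0.177 against a true 0.113 to 0.179 against 0.203. Power is lost when schools change alike, the errors roughly cancel in mid-range, and type I error exceeds 5% when schools change differently or r is low.

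Two stronger readings are not supported. A reader might infer that the plan inflates false positives throughout; in much of the range it is conservative. A reader might also infer that baseline-adjusted regression is the only proper remedy. That analysis relies on random allocation, which the SAP title states, while IRB 7 says that "seven schools would serve as matched comparison sites" and describes no random allocation. The documents do not settle which applies.

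This should be corrected before analysis. It does not invalidate the design.

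**What to change.** Change the SAP wording for ID-linked outcomes:

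1. Keep the group x time contrast and the school effect. Add a random intercept for child within school (or an unstructured within-child covariance) **and** a school-by-time random effect. Do not add the child intercept alone.
2. Test on (schools analysed minus 2) degrees of freedom, whatever the estimated school variance. That is 12 only if all 14 schools pass the adherence rule.
3. If the team confirms that schools were randomised, it may instead pre-specify follow-up regressed on the child's own baseline, group and covariates, with a school random intercept and the same degrees of freedom. These are different estimators, so the SAP must name one.
4. For any primary outcome that cannot be linked by child, use a school-level test of mean change on the same degrees of freedom.
5. State which measures are primary, which carry the study ID across semesters, and whether schools were randomised, matched or both.

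**Cost.** No new data are needed. Intervals widen where schools change differently: at a share of 100% (r = 0.6) the true standard error is 0.203 against a reported 0.179, and power of the change test is 39% against a nominal 54% that comes with 8.4% type I error. With complete pairs, simulated over r = 0.3 to 0.8 and several school-size patterns, type I error was 1.6–5.2% for the model in item 1 (fitted through its change-score equivalent) and 4.7–5.2% for the school-level test. No such claim is made for incomplete data.

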#### Response:

We will recruit all 14 of the after school program schools in xxx Schools to participate in the research. Seven of the schools will receive an intervention in year one and the other seven schools will receive in year two. All schools will participate in assessments during both the fall and spring each year.

We will work with the xxx Schools after school program coordinator to send a recruitment email ( staff\_email\_05.15.22) to the program leaders at the 14 schools. Once the leader agrees to participate, they will send informed consents/assents to parents/guardians of the students in the after school program.

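### The SAP tests intervention against control at every follow-up, but by spring of year 2 all 14 schools have been exposed and no untreated comparison remains

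*SAP*

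**What the plan says.** The SAP, under Data analysis, states: "Intervention effects on the primary trial outcomes (at each follow-up time point) will be assessed using general linear mixed effects models". The model has group, a two-level time factor and their interaction as fixed effects, and school as a random effect. It adds: "Separate analyses will be performed at each follow-up time point". The SAP does not name the baseline wave or the follow-up waves, does not restrict the comparison to year 1, and does not mention that the comparison schools later start the intervention.

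The schedule is in the Protocol.

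- IRB 6 (Recruitment Methods): "Seven of the schools will receive an intervention in year one and the other seven schools will receive in year two". On measurement: "All schools will participate in assessments during both the fall and spring each year".
- IRB 7 (Study Procedures): "We are using a crossover pre/post study design", in which "seven after-school programs would receive the intervention in years 1 and 2 and seven schools would serve as matched comparison sites". Then: "During year two, the next seven schools would receive the intervention". Peer leaders are trained in the fall semesters of 2022 and 2023.
- IRB 7, on accelerometry: the first seven schools are measured four times, the other seven only in the year in which they serve as controls.
- IRB 8 (Compensation): everyone takes part in both years, as comparison or as programme participant. It does not say which applies in which year.

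**The concern.** A group-by-time interaction estimates an intervention effect only while one group is untreated. The Protocol ends that state during year 2, yet the SAP applies the same contrast, under the same label, to every follow-up.

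The Protocol also disagrees with itself about the first seven schools. IRB 7 treats them in both years; IRB 6 mentions year 1 only. If they continue, the spring 2024 contrast is early versus delayed exposure. If they stop, it sets previously treated schools against newly treated ones and is affected by carry-over. On neither reading is there an untreated control.

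Followed as written, the plan would report the year-2 estimate on primary outcomes with the same standing as the year-1 estimate. On several readings an intervention that works would give a zero or negative figure, simply because the comparison schools had been treated too. That could be read as loss of effect or as harm.

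**Working it through.** **1. Waves.** Fall and spring in two years, starting in fall 2022, give fall 2022, spring 2023, fall 2023 and spring 2024. A single fall 2022 baseline leaves three follow-ups. A fall baseline within each year leaves two, spring 2023 and spring 2024. Spring 2024 is a follow-up either way. Year 1 alone has one follow-up, so a rule for separate analyses at each follow-up cannot refer to year 1 only.

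**2. Exposure.** Untreated schools at spring 2023: 7. Schools exposed by spring 2024: 7 + 7 = 14 of 14, so untreated = 0. This count needs no assumption about effect size.

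**3. Size of the distortion (illustrative).** Assume that:

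- the first-year effect is d in both sets of schools;
- the first seven carry the full d into fall 2023;
- the delayed seven are measured before training in fall 2023;
- g is the share of d that the first seven add in year 2 if they continue, and r the share they retain if they stop, each from 0 to 1.

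None of these values is in the documents. Spring 2024 levels are then d in the delayed seven, and (1+g)d (continue) or r×d (stop) in the first seven. The contrast is first seven minus delayed seven, in change from baseline:

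| First seven in year 2 | Baseline | Contrast | At 0, 0.5, 1 |
|---|---|---|---|
| Continue | Fall 2022 | (1+g)d − d = g×d | 0, 0.5d, d |
| Continue | Fall 2023 | [(1+g)d − d] − d = (g−1)d | −d, −0.5d, 0 |
| Stop | Fall 2022 | r×d − d = (r−1)d | −d, −0.5d, 0 |
| Stop | Fall 2023 | [r×d − d] − d = (r−2)d | −2d, −1.5d, −d |

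The same d gives anything from +d to −2d, and the contrast equals d only at g = 1 with a fall 2022 baseline.

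**4. Coding by current condition instead.** If the first seven continue, year 2 has 14 intervention and 0 control schools, and the group term is not estimable. If they stop, it is 7 versus 7 and the last two rows change sign: (1−r)d, from 0 to +d, and (2−r)d, from +d to +2d. The seven schools labelled control were treated in year 1. This equals d only at r = 0 (fall 2022 baseline) or r = 1 (fall 2023 baseline).

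**5. Accelerometry (IRB 7).** First seven: 7 × 4 = 28 school-waves. Delayed seven: 7 × 2 = 14, all in year 1. In year 2 that is 7 × 2 = 14 versus 0, so no between-arm contrast exists. If the IRB 6 statement that all schools are assessed in every semester covers accelerometry, step 3 applies to it as well.

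**6. The SAP's sample size figure.** The SAP plans 147 versus 147 students in 7 versus 7 schools, ICC 0.05, and a detectable effect of 0.370 at 80% power. With 147/7 = 21 per school, the standard error is √[2(0.05 + 0.95/21)/7] = 0.165 and the two-sided detectable effect is (1.960 + 0.842) × 0.165 = 0.462. So 0.370 is not reproduced from these inputs. That is a separate matter and the present point does not depend on it.

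**The case against.** The SAP does not define its follow-ups. That spring 2024 is one of them is inferred from the Protocol's schedule, so it can be argued that the plan is incomplete rather than wrong. But spring 2024 is a scheduled assessment on either baseline, and year 1 cannot supply more than one follow-up. The rule as written therefore reaches a wave without untreated schools.

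The range in multiples of d is open to more criticism. It assumes coding by original arm; under current-condition coding the rows for stopping change sign. The −2d extreme needs full carry-over to fall 2023 and none left by spring 2024. Support for stopping is thin: IRB 6 does not say that the first seven schools stop, and IRB 7 says they are treated in both years. If they continue, original-arm coding gives −d to +d, and a negative value arises only with a baseline reset to fall 2023. All of this stands, and the range should be read as illustrative. The count of zero untreated schools does not rest on it.

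For accelerometry, the restriction in IRB 7 already prevents a mislabelled year-2 estimate. That also stands, but the SAP still calls for a test that cannot be run.

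Finally, a model with exposure varying over time could use the delayed schools' year-2 change. A single 7-versus-7 contrast with 21 students per school and ICC 0.05 has only about 61% power for 0.370 (normal approximation, no covariate gain). This is a fair reason to consider such a model. The SAP, however, specifies no such model.

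**Conclusion.** The concern holds and should be fixed before analysis. By spring 2024, 14 of 14 schools have been exposed, so the planned intervention-versus-control contrast at that wave does not estimate an intervention effect under either description of the first seven schools. A larger sample would not cure this, because the fault lies in what is being estimated.

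The documents do not determine the size. The range from +d to −2d rests on original-arm coding and on assumed values of g, r and carry-over. The spring 2023 contrast is not affected by this problem. Fall 2023 is uncertain, because the Protocol does not say whether that assessment precedes training at the delayed schools.

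**What to change.** In the SAP:

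1. Restrict the confirmatory intervention-versus-control contrast to year 1: fall 2022 baseline, spring 2023 follow-up.
2. Label year-2 comparisons as early versus delayed exposure, or as within-arm maintenance and replication, and not as the intervention effect. Use fall 2023 as a between-arm contrast only if it is measured before the delayed schools are trained.
3. State that accelerometry has no year-2 between-arm analysis under the IRB 7 collection plan.
4. Reconcile Protocol IRB 6, IRB 7 (design and accelerometry) and IRB 8 in one table showing, for each semester, which schools are exposed and which are measured on which outcome.

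A pooled two-year model with exposure duration is optional. If it is used, its exposure and carry-over terms should be specified in advance.

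The cost is SAP wording and one table, with no new data. The year-1 comparison keeps 7 versus 7 schools and 147 versus 147 students, so the planned sample does not change. What is lost is a between-arm estimate of the intervention effect beyond year 1, which this design cannot supply. Unless the pooled model is specified, the delayed schools' year-2 change also stays out of the effect estimate.

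### The only analysis population in the plan is schools reaching 80% adherence, a measure that these documents do not define and that can be seen only after allocation; no analysis of all 14 schools as allocated is planned.

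*SAP*

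**What the plan says.** The SAP's Data analysis section sets out mixed models for the primary outcomes, with group, time and their interaction as fixed effects and school as the random effect. The same paragraph adds three sentences that matter here:

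- on the school-level outcomes, "Analysis related to attendance and behavioral change will be performed with the school as the level of analysis";
- on timing, "Separate analyses will be performed at each follow-up time point";
- on who is analysed, "Schools will be included in analyses if they meet at least 80% adherence to the protocol".

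The last is not labelled per-protocol, secondary or sensitivity, and no other analysis population is given.

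Related terms appear only among the secondary implementation outcomes. Fidelity is to be described from "data from monthly observations (fidelity and sustainability"), and adherence is one heading for sorting interview data, in a list of "dimensions (adherence, exposure/dose, quality of delivery, component differentiation, and participant involvement"). Neither is tied to the 80% figure.

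In the Protocol, section 6 (Recruitment Methods) gives the allocation: "Seven of the schools will receive an intervention in year one and the other seven schools will receive in year two". It adds that "All schools will participate in assessments during both the fall and spring each year". Section 7 (Study Procedures) agrees on the second group: "During year two, the next seven schools would receive the intervention".

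**The concern.** Adherence to a trial protocol can be observed only once the trial is running. A rule that admits schools by adherence therefore selects clusters after allocation, and whatever comparability the allocation gave is no longer assured. With seven schools per arm, one exclusion removes a seventh of an arm.

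The missing definition adds to this. If adherence means delivery of the curriculum, then in year 1 the rule can act only on the intervention arm, because the other seven schools have nothing to deliver. If it means completing assessments, it acts on all 14. These readings give different analysis sets, and nothing in the two documents stops the choice between them from being made after outcomes are known. The rule also covers the attendance and behaviour analyses, where each excluded school is a lost observation. Because each follow-up is analysed separately, the set of schools could differ between time points if adherence is scored up to each one.

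**Working it through.** **1. Is there any other analysis set?** The SAP's Data analysis section gives one population, the 80% rule. Its Sample size calculation section counts 7 intervention and 7 control schools and makes no allowance for excluded schools. Protocol section 6 has every school assessed, but that describes data collection and not who is analysed. Neither document plans an all-schools analysis, even as a sensitivity analysis.

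**2. The plan's own figure.** Inputs from the Sample size calculation section: 294 students in 14 schools, so m = 21 per school; ICC 0.05; 80% power; alpha 0.05 (taken as two-sided, since the side is not stated); detectable effect 0.370.

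- Design effect: 1 + (21 − 1) × 0.05 = 2.0.
- Standard error at 7 v 7: sqrt((2.0/21) × (1/7 + 1/7)) = 0.165.
- Detectable effect: (1.960 + 0.842) × 0.165 = 0.462 (normal), or 0.503 with t on 12 df.
- Power at 0.370: Φ(0.370/0.165 − 1.960) = 61% (normal), or 54% (t).

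The 0.370 is not reproduced from these inputs. That is a separate matter. It means only that the loss below is best given as a ratio, which does not depend on 0.370.

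**3. Precision lost when schools are dropped.** For k intervention and c control schools of equal size, the detectable effect relative to 7 v 7 is

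ratio = sqrt((1/k + 1/c) / (2/7)).

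For the t version, multiply by the sum of the 97.5% and 80% t quantiles on k + c − 2 df, divided by the same sum on 12 df (3.051).

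| Schools analysed | (1/k + 1/c)/(2/7) | Ratio, normal | t sum (df) | Ratio, t |
|---|---|---|---|---|
| 6 v 7 | 1.083 | 1.041 | 3.077 (11) | 1.05 |
| 5 v 7 | 1.200 | 1.095 | 3.107 (10) | 1.12 |
| 4 v 7 | 1.375 | 1.173 | 3.146 (9) | 1.21 |
| 6 v 6 | 1.167 | 1.080 | – | – |
| 5 v 5 | 1.400 | 1.183 | – | – |

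The number dropped is assumed, as the documents give no basis for one. The t version is the natural one for the school-level outcomes.

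**4. When does the rule bias the estimate?**

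- *No true effect.* Bias arises only if adherence is linked to a school's change over time. As an illustration, assume a school-level correlation of 0.8 between baseline and follow-up. The SD of school change is then sqrt(2 × 0.05 × (1 − 0.8)) = 0.141. Drop the two least adherent of seven: the mean adherence of the five kept is 0.42 SD above average. With a correlation r between adherence and change, the bias is r × 0.42 × 0.141, which is 0.018 SD at r = 0.3 and 0.042 SD at r = 0.7. It has the opposite sign if r is negative, and is zero if school effects are fully stable or no school fails.
- *A true effect that grows with delivery.* The average effect over the best-delivering schools exceeds the average over all seven. Dropping poor deliverers then raises the estimate even when school effects are fully stable. This is a change in what is estimated, and its size cannot be derived from the documents.

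**The case against.** The strongest defence is that the rule may do nothing. Every school may reach 80%, and the illustrated bias with no true effect is at most 0.042 SD. The cut-off was also set ahead: the SAP is dated June 20, 2022, before the Fall 2022 training described in Protocol section 7. The curriculum and assessment attachments are not part of these documents and may say how adherence is scored. All of this stands. It confines the point to an undefined measure in these two documents and an exclusion whose effect is conditional. It does not supply an as-allocated analysis.

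A second objection is that allocation may offer limited protection here. The SAP title says cluster randomized, while Protocol section 7 describes a crossover pre/post design with matched comparison sites, and no randomisation method is given. That is why this point speaks of schools as allocated. Dropping schools for poor adherence would disturb a matched comparison too.

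Third, if adherence means completing assessments, an excluded school may have no outcome data, and an all-schools analysis would recover little. This also stands.

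Some stronger readings are tempting, but the documents do not support them:

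- *The rule favours the programme.* The direction depends on how adherence relates to change, which is not stated.
- *Power falls from 80% by a given amount.* The stated inputs do not give 80% at 0.370 (step 2), so power figures that start from 80% would not be this trial's.
- *Type I error is inflated to a given rate.* The SAP's model has school as its only random effect, with no child or school-by-time term. A rate worked out for a model with those terms would not describe the planned test.

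**Conclusion.** The point holds, and the plan should be changed before analysis. As written, the primary analysis and the school-level attendance and behaviour analyses are restricted by a variable that arises after allocation and that these documents leave undefined, with no all-schools analysis to fall back on. If any school fails, the estimate no longer answers what assigning the programme achieves.

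The size that can be stated is the precision cost: about 4%, 10% or 17% on the detectable effect (5%, 12% or 21% with t) for one, two or three intervention schools lost. If the rule acts on both arms, it is about 8% at 6 v 6 and 18% at 5 v 5 (normal). These figures assume equal school sizes and a number of failing schools that is unknown and may be zero. The seriousness rests on the choice of analysis set and the missing definition, not on the bias illustration.

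**What to change.** Amend the SAP's Data analysis section as follows.

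1. **Primary analysis:** all 14 schools in the group allocated, whatever their adherence. Use all children with available outcome data for the child-level outcomes, and all schools with data for attendance and behaviour. If children with only one measurement are included, add a child random effect; without it the planned model makes no use of the within-child correlation.
2. **Period:** apply this to the time in which the second seven schools are still controls. In year 2 they also receive the programme, and Protocol section 7 plans accelerometry in those schools only for their control year.
3. **The 80% rule:** keep it for a secondary per-protocol or sensitivity analysis, labelled as not protected by allocation. Before outcome data are seen, define for each arm what adherence covers, how it is scored and over what period.
4. **Reporting:** list excluded schools by arm and time point.

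The cost is two or three sentences, a short definition and one extra model run. All schools are already due to be assessed each fall and spring, so no new data collection is needed. The downsides are that the primary estimate may be smaller if delivery is poor, and that little is gained where an excluded school has no outcome data.
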